7.2. Implementation, data collection and monitoring procedures

7.2.1. Assessments

7.2.1.1 Screening Assessments

The assessments listed in Table 5 will be performed to determine if a subject can participate in the study.

The **first investigation** performed will be the measurement of HCV RNA load to assess the need for treatment. Only patients with detectable HCV RNA load will continue to be assessed for potential participation in the study.

Table 5: Screening assessments

Category	Examination
Virology	HCV RNA load
Medical history	Interview and/or chart review
Liver imaging	Fibrosis assessment by transient elastography Liver ultrasound exam
Clinical chemistries	SGPT/ALT, SGOT/AST, gamma glutamyl transferase, bilirubin (conjugated, unconjugated), Albumin, Alkaline phosphatase, glucose, triglycerides, prothrombin time (PT), HDL & LDL cholesterol, alpha fetoprotein (AFP), creatinine, urine protein, thyroid-stimulating hormone (TSH), vitamin D level
Hematology	CBC including platelets
Ophthalmology	Ophthalmologic examination (fundus) if diabetes mellitus or hypertension
Central nervous system	Beck Inventory Depression scale (nurse, counselor)

Heart, lungs	Electrocardiogram, chest X-ray,
Contraception	Pregnancy test (for female participant or partner of male participant) if childbearing age
Host genetic	IL28B polymorphism

7.2.1.2 Assessments during the study

The detailed assessments are listed in Table 6.

Fibrosis assessment. For enrollment, fibrosis assessment will be performed using the transient elastography ultrasound based technique. It measures the stiffness of the liver, which is well correlated with the fibrosis stage assessed by liver biopsy. It has been extensively used as a non-invasive method for detection of cirrhosis in patients with chronic liver disease (Foucher et al., 2006). In addition, to further characterize patients enrolled in this study, two scores will be calculated:

- the AST to platelets ratio index (APRI score) will be calculated at baseline as it has been shown to predict both significant fibrosis and cirrhosis in patients with chronic hepatitis C (Wai et al., 2003).
- The FIB4 score (Bruno et al., 2011), which has also been used for the evaluation of fibrosis. A cut-off value >3.25 is consistent with significant (F2–F4) fibrosis; its sensitivity was 70% and specificity 86–97% in a study conducted in HIV/HCV co-infected persons (Sterling et al., 2006). It is calculated using the following formula:

$$(\text{age [years]} \times \text{AST [U/L]}) / (\text{platelet count} [\times 10^9/\text{L}] \times (\text{ALT [U/L]}^{1/2}))$$

Depressive symptoms will be screened using the Beck Depression Inventory (Thai version). This auto-administered scale, which consists of 21 questions to assess the severity of depression, has been extensively used in various studies related to HCV treatment.

Table 6: Follow up Assessments

	Scr.	Baseline	Wk2	Wk4	Wk8	Wk12	Wk16	Wk20	Wk24	Wk28	Wk32	Wk36	Wk40	Wk44	Wk48	6 months post-Treatment
HCV RNA load	X			X		X			X						X	X
Counseling	X	X	X	X					X						X	X
Beck's Depression Inventory scale (more often if necessary, see Section 7.2.2.2, page 20)	X			X		X			X			X			X	
SF-36 Scale (quality of life)		X							X						X	X
Pregnancy test (for female participant or partner of male participant) if childbearing age	X	X		X	X	X	X	X	X	X	X	X	X	X	X	X
CBC with differential	X	X	X	X	X	X	X		X		X		X		X	X
SGPT (ALT)	X	X		X		X		X		X		X		X	X	X
Alkaline phosphatase, albumin, bilirubin (conjugated, unconjugated), gamma-glutamyl-transferase (GGT), HDL, LDL cholesterol, triglyceride, prothrombin time, SGOT (AST), proteinuria (random)	X														X	X
Electrolytes (Na+, K+, Cl-, HCO3-)		X				X			X						X	
Creatinine	X	X		X	X	X		X		X		X			X	X
Glucose	X	X				X			X						X	
TSH	X	X							X						X	
Alpha fetoprotein (AFP), Vitamin D, IL28B polymorphism, HCV genotype	X															
Chest X-Ray, Electrocardiogram, Abdominal sonogram, Ophthalmologic examination (fundus) if diabetes mellitus or hypertension, Fibrosis assessment	X															
Ribavirin plasma level (further assessments as needed)			X	X												
Plasma and cell pellets collection & storage	X	X	X	X	X	X	X	X	X	X	X	X	X	X	X	X
CRF completion	X	X	X	X	X	X	X	X	X	X	X	X	X	X	X	X
Total blood volume (mL)	20	8	6	9	6	18	3	3	18	3	3	3	3	3	20	18

7.2.2. Safety procedures

7.2.2.1 Anemia

Monitoring

Anemia, the most frequent side effect of ribavirin, will be carefully monitored (see Table 6).

Grade 4 will be immediately reported to the PHPT coordination center.

Management

The principles for the management of anemia will be based on “Guide for evaluation and treatment of Hepatitis C in adults co infected with HIV” (Sulkowski, Cheever, & Spach, 2011).

“The initial and primary management of symptomatic anemia (hemoglobin level below 10 g/dL) is ribavirin dose reduction. The ribavirin dose reduction most often consists of a gradual two-step process:

- **Step 1:** reduce by 200 mg for patients receiving 800-1200 mg/day or reduce by 400 mg for patients receiving 1400 mg/day;
- **Step 2:** reduce by another 200 mg if the hemoglobin level has not improved 2 weeks after step 1 reduction (and if the patient’s current dose is 800 mg or greater). If the patient has a sharp decline in hemoglobin, particularly during the first 4 weeks of therapy, or the patient has moderate to severe symptoms from the anemia, most experts would recommend immediately reducing the ribavirin dose to 600 mg/day (without a step-wise reduction).
- The ribavirin dose should not be reduced to lower than 600 mg/day.
- Patients undergoing ribavirin dose reduction should have close monitoring of hemoglobin level levels, typically every 1-2 weeks; the frequency of monitoring can decrease when the hemoglobin level improves and stabilizes. Ribavirin should then remain at the reduced dose.”
- Treatment discontinuation should be considered in case of persisting severe anemia or major clinical consequences of anemia.”

[figure not shown]

Figure 2: Dose reduction for the management of anemia

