Dry skin/ rashes	
 • Avoiding long, hot showers or baths • Using moisturizing soaps • Using moisturizing lotion after showers • Using mild unscented laundry detergents and avoiding fabric softeners • Using sunscreen • Trying rubbing or pressing on the itchy areas rather than scratching • Prescribe petroleum jelly or other agents on dry, itchy areas
Hair thinning or hair loss	
 • Avoiding harsh hair products such as dyes, perms, gels, sprays and mousses • Using a mild shampoo such as baby shampoo • Avoiding braiding hair; using a wide-tooth comb or soft brush • Wearing a cap, scarf, turban or wig
Injection site reactions	
 • Before injecting, warming the medicine by gently rolling the syringe in the hands for a minute • Rotating/alternating the injection site - thigh, upper arm and abdomen. If thin, using the thigh area might help • Not doing injection into an area that is irritated, bruised or red • Not doing rub injection site • Applying a cold pack • Hydrocortisone cream or other medications can be prescribe to help

Modification of treatment in case of laboratory abnormality:

Peg-interferon alfa-2b must be stopped if: Laboratory exam	Value	Yes	Dose modification
Hemoglobin	< 8.5 g/dL		→ STOP Peg-interferon in case of any of these events
Hemoglobin if history of stable cardiac disease * 4 weeks of a dose reduction	< 12 g/dL*		
WBC	< 1000/mm ³		
Neutrophils	< 500/mm ³		
Platelets	< 25000/mm ³		

Laboratory exam	Value	Yes	Dose modification
Hemoglobin if history of stable cardiac disease	≥ 2 g/dL decrease since the last visit		→ Reduce dose of Peg-interferon of 0.5 mcg/kg If one of these events is verified
WBC	< 1500/mm ³		
Neutrophils	< 750/mm ³		
Platelets	< 50000/mm ³		

Ribavirin dose reduction

Laboratory exam	Value	Yes	Dose modification
Hemoglobin	< 10 g/dL		→ Reduce dose of Ribavirin If one of these events is verified
Hemoglobin if history of stable cardiac disease	≥ 2 g/dL decrease since last visit		

Dose reduction:

If previous dose = 400 mg morning/200 mg evening → **STOP Ribavirin and contact** ☎

If previous dose = 400 mg morning/400 mg evening → Decrease to 400 mg morning/200 mg evening

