
If previous dose = 600 mg morning/400 mg evening → Decrease to 400 mg morning/400 mg evening

If previous dose = 600 mg morning/600 mg evening → Decrease to 600 mg morning/400 mg evening

If previous dose = 600 mg morning/800 mg evening → Decrease to 600 mg morning/400 mg evening

☎: If Ribavirin dose has already been reduced two times but the listed laboratory abnormalities persist, please contact: [name], [name]

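### For patients on ribavirin 1000, 1200 or 1400 mg/day with a sharp hemoglobin fall or marked anemia symptoms, section 7.2.2.1 and Appendix 4 give different next doses, and neither is said to govern

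*Combined protocol and SAP*

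**What the plan says.** Section 7.2.2.1 (Anemia, Management) takes its rules from a published co-infection treatment guide: "The principles for the management of anemia will be based on" that guide, which it then quotes. The ordinary route is step-wise. Step 1 is to "reduce by 200 mg for patients receiving 800-1200 mg/day or reduce by 400 mg for patients receiving 1400 mg/day", and a second 200 mg reduction follows if hemoglobin has not improved after two weeks. An exception comes next, introduced by "If the patient has a sharp decline in hemoglobin, particularly during the first 4 weeks of therapy, or the patient has moderate to severe symptoms" of anemia. In that case "most experts would recommend immediately reducing the ribavirin dose to 600 mg/day (without a step-wise reduction").

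Appendix 4 has a tick-box table for laboratory abnormalities. Its ribavirin part is triggered by hemoglobin below 10 g/dL or, in patients with a history of stable cardiac disease, by a fall of at least 2 g/dL since the last visit. Either trigger leads to the same list, which has one next dose for each previous dose:

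- from 800 mg/day: "If previous dose = 400 mg morning/400 mg evening → Decrease to 400 mg morning/200 mg evening"
- from 1200 mg/day: "If previous dose = 600 mg morning/600 mg evening → Decrease to 600 mg morning/400 mg evening"
- from 1400 mg/day: "If previous dose = 600 mg morning/800 mg evening → Decrease to 600 mg morning/400 mg evening"

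The entry for 1000 mg/day leads to 400 mg twice daily. No entry depends on symptoms or on how fast hemoglobin fell, apart from the cardiac trigger. The list foresees repeated reductions and asks the site to make contact if the abnormality persists after two.

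Section 7.3 sets the starting doses. Genotypes 2 and 3 start at 800 mg/day, as do genotypes 1, 4, 5 and 6 in the lowest weight band (below 65 kg). Genotypes 1, 4, 5 and 6 start at 1000, 1200 or 1400 mg/day in the bands from 66 kg up.

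**The concern.** The exception in section 7.2.2.1 is written for acute or clearly symptomatic anemia. The Appendix 4 list has a form that a site could complete at a visit, yet it has no entry for that case. A site investigator who follows the section and one who follows the appendix can reach different doses for the same patient on the same day.

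Patient safety is the main issue, since ribavirin anemia is the toxicity the protocol monitors most closely. The analysis could also be affected. Objective 5 concerns discontinuation for tolerance or safety, and objective 6 relates ribavirin concentration to anemia. If the dose after an anemia event depends on which page was read, part of the variation in exposure comes from the wording of the protocol and not from the patient.

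**Working it through.** No sample-size, power or error-rate figure is involved. The check is dose arithmetic on the two rules.

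**Step 1: do the ordinary rules agree?** The first step of section 7.2.2.1 is the previous dose minus 200 mg for 800 to 1200 mg/day, and minus 400 mg for 1400 mg/day. This gives 800 − 200 = 600, 1000 − 200 = 800, 1200 − 200 = 1000 and 1400 − 400 = 1000. Appendix 4 gives 600, 800, 1000 and 1000. The two match at every dose, so the list reproduces the ordinary step and any disagreement lies in the exception alone.

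**Step 2: the exception against Appendix 4.** The difference is the Appendix 4 next dose minus 600 mg/day, for an event that meets both the exception and an Appendix 4 trigger.

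| Previous dose (mg/day) | 7.2.2.1 exception | Appendix 4, one event | Difference | Ratio |
|---|---|---|---|---|
| 800 | 600 | 600 | 0 | 1.00 |
| 1000 | 600 | 800 | +200 | 800/600 = 1.33 |
| 1200 | 600 | 1000 | +400 | 1000/600 = 1.67 |
| 1400 | 600 | 1000 | +400 | 1000/600 = 1.67 |

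**Step 3: how many Appendix 4 reductions lead to 600 mg/day?**

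- 800 → 600: one.
- 1000 → 800 → 600: two.
- 1200 → 1000 → 800 → 600: three.
- 1400 → 1000 → 800 → 600: three.

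**Step 4: is Appendix 4 merely silent on rapid falls?** Not entirely. Its cardiac-history trigger is a rapid fall, and it feeds the same single-step list. Take a patient with stable cardiac disease on 1200 mg/day whose hemoglobin drops by 2 g/dL or more between visits. Appendix 4 gives 1000 mg/day. If that drop counts as a sharp decline, which section 7.2.2.1 does not define, the exception gives 600 mg/day.

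**Step 5: who can be affected?** Under section 7.3, only genotypes 1, 4, 5 and 6 in the bands from 66 kg up start above 800 mg/day. The documents give neither the weight distribution nor the genotype mix of the study population, so the number among the 60 planned patients (15 in the first part) cannot be derived. Section 4.2 names genotypes 3 and 6 as predominant in Southeast Asia. One of these is outside the affected group and the other can be inside it.

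**Step 6: could the ribavirin levels be affected?** Table 6 schedules levels at weeks 2 and 4, with more as needed, and blood counts at the same weeks. A reduction prompted by a fall first seen at week 4 comes after the last scheduled level. Of the scheduled levels, only the week 4 sample could be altered, and only by an event found by about week 2.

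**The case against.** The best reply is that this is an omission and not a contradiction. The exception is reported as what most experts advise, within guide text adopted as principles, so it is softer than a protocol order. Appendix 4 is headed as a response to laboratory abnormalities, so the lack of a symptom row is unsurprising. Section 7.2.2.3 points to the appendix for other adverse events and calls its content recommendations. Section 7.2.2.1 is the dedicated anemia section, and section 8.3.2 refers dose decisions to expert advice. Figure 2, on dose reduction for anemia, is not shown in the text reviewed and may carry the exception.

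Much of this stands, and it rules out several stronger readings that a reader might infer:

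- *Appendix 4 permits only one step.* It lists one step per event, foresees further ones and does not prohibit a larger reduction.
- *All patients with acute anemia are left on a higher dose.* At 800 mg/day the two places agree, and many patients may start there.
- *Sites will differ in exposure, and response will suffer.* No passage says that sites use the appendix in place of the section. The documents support no estimate of an effect on response or discontinuation, and section 7.4.1 describes the ribavirin analysis as descriptive.

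The reply does not remove the conflict itself. Appendix 4 has explicit hemoglobin triggers and a definite next dose for each previous dose, one trigger is a rapid fall, and neither place cross-refers to the other or is given precedence. Whatever Figure 2 shows, the Appendix 4 text would still differ from section 7.2.2.1.

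**Conclusion.** The protocol contains an internal inconsistency, limited to ribavirin doses of 1000, 1200 and 1400 mg/day. For an event that meets the exception in section 7.2.2.1 and also triggers the Appendix 4 list, the appendix dose is 200, 400 and 400 mg/day higher, or 33%, 67% and 67% above 600 mg/day. At 800 mg/day there is no difference.

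The conclusion assumes that both texts are in force, because no precedence is stated. It makes no assumption about the content of Figure 2. The number of patients concerned is unknown, and any effect on sustained response, discontinuation or ribavirin levels is possible but unquantified. The point merits correction because it concerns the management of a safety event and is cheap to fix, not because a bias in the primary result has been shown. No view is taken on which dose rule is right.

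**What to change.** Reconcile the Appendix 4 ribavirin list with section 7.2.2.1, and Figure 2 if needed, so that the same event leads to the same next dose in each place. Alternatively, add a sentence saying which governs. The investigators decide which rule stands.

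Two further steps would help but are secondary. If the exception is kept, state what counts as a sharp decline. Record the reason for each ribavirin reduction on the case report form, if it does not already ask for it; the form is not among the documents, so this could not be checked.

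The cost is one text edit and at most one form item, with no extra visits or tests. Under section 8.3.1 the modification goes to the ethics committees before use.

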7.2.2.2. Depression

Monitoring

A common side effect of peg-interferon is depression. The study nurse will be trained before the beginning of the study to specifically search for signs and/or symptoms of depression. The screening for depression and other side effects will be performed at every visit. In addition, the Beck's Depression Inventory (BDI) will be used to screen for depression at the screening visit, 4, 12, 24, 36 and 48 weeks after the beginning of treatment and more frequently if needed.

A BDI score greater than 20 should be immediately reported to the PHPT coordination center.

Management

Mild depressive symptoms during treatment do not typically require peg-interferon dose reduction or treatment discontinuation. In case of any mild depressive symptoms, more frequent monitoring of depression severity will be implemented, typically once weekly by visit or phone. Antidepressants, such as selective serotonin re-uptake inhibitors, will be prescribed and specialized advice sought as necessary.

Moderate or severe depression mandates an evaluation by a mental health professional (e.g., psychiatrist, clinical psychologist) and dose reduction of peg-interferon (peg-interferon alfa-2b from 1.5 to 1.0 mcg/kg). In some cases, a larger initial peg-interferon dose reduction may be needed (reduce peg-interferon alfa-2b from 1.5 to 0.5 mcg/kg). Importantly, all persons found to have moderate or severe depression should be evaluated for suicidal ideation. For patients suffering from severe depression or active suicidal ideation, peg-interferon injection (and ribavirin treatment) will be discontinued and the patient will be explained that this treatment cannot be administered in his/her case. Medical follow up will continue. For the study, the evolution of depression will be documented as completely as possible but study procedures will be adapted to the case. In some cases, patients may require hospitalization for management.

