Depression	
 • If mild depression symptoms (according to the Beck scale): 
 ○ Encourage patients to talk about their symptoms and to take medications that might help (if indicated) ○ Encourage discussion about thoughts of harming him/herself or someone else ○ Encouraging patients to go to the nearest emergency room if feeling in danger of harming him/herself or others ○ Advising to do mild to moderate exercises at least 3 times/week as directed by your provider ○ Increase monitoring frequency of depression evaluation ○ Prescribe antidepressant if necessary and seek for specialized advice • If moderate to severe depression symptoms (according to the Beck scale): 
 ○ Evaluate for suicidal ideation and seek specialized advice ○ Decrease the dose of peg-interferon from 1.5 to 1.0 mcg/kg or less

Side Effect	Recommendations and prescription for the patient
	
 ○ If, severe depressive symptoms or suicidal ideation: discontinue HCV treatment
Anxiety and irritability	
 • Recommend talking to healthcare personnel about symptoms and medications that might help • Recommend always discussing with healthcare personnel thoughts of harming him/herself or someone else • Recommend going to the nearest emergency room if in danger of harming him/herself or others • Recommend doing mild to moderate exercises at least 3 times/week if possible • Recommend trying relaxation techniques such as deep breathing, taped exercises, yoga, Tai Chi or meditation • Recommend avoiding stimulants like caffeine and maintaining adequate fluid intake
Insomnia	
 • Recommend going to sleep and waking up at the same time every day • Recommend to not read or watch TV in bed • Recommend limiting daytime naps • If experiencing anxiousness after ribavirin intake, recommend taking at 4-5 pm instead of before bedtime • Recommend limiting fluid intake for 2 hours before bedtime to avoid having to get up to go to the bathroom • Recommend avoiding caffeinated products, especially in the afternoon and at night • Recommend avoiding heavy meals close to bedtime • Recommend taking warm baths, reading or listening to music, getting a massage • Recommend trying a glass of warm milk (contains tryptophan, a natural sleep agent) • Prescribe diphenhydramine or other medications if indicated

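### The stop rule for suicidal ideation reads differently in Section 7.2.2.2 ('active' ideation) and Appendix 4 (no qualifier), and the protocol does not say which text governs

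*Combined protocol and SAP*

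**What the plan says.** Section 7.2.2.2 handles depression in two steps. On mild symptoms it says: "Mild depressive symptoms during treatment do not typically require peg-interferon dose reduction or treatment discontinuation". A separate paragraph then covers more serious cases. It begins "Moderate or severe depression mandates an evaluation by a mental health professional" and calls for lowering peg-interferon from 1.5 to 1.0 mcg/kg, or to 0.5 in some cases. It goes on: "Importantly, all persons found to have moderate or severe depression should be evaluated for suicidal ideation". The stop rule comes directly after that: "For patients suffering from severe depression or active suicidal ideation, peg-interferon injection (and ribavirin treatment) will be discontinued". The patient is then told that this treatment is not possible in his or her case.

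The depression row of Appendix 4 is built the same way. One bullet opens "If mild depression symptoms (according to the Beck scale"; among its instructions is "Encourage discussion about thoughts of harming him/herself or someone else", and it contains no stop line. The next opens "If moderate to severe depression symptoms (according to the Beck scale" and lists evaluation for ideation, a dose decrease to 1.0 mcg/kg or less, and then: "If, severe depressive symptoms or suicidal ideation: discontinue HCV treatment".

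Section 7.2.2.3 points to Appendix 4 for recommendations on managing clinical side effects. Section 7.1.3 allows treatment to be stopped for severe or intolerable adverse effects in general terms and does not mention suicidal ideation.

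**The concern.** These are two current instructions on the same safety decision, with different triggers. Within Section 7.2.2.2 itself, staff are told to evaluate for ideation without a qualifier, and the next sentence stops treatment only if the ideation is active. A careful reader can conclude that the stop is meant to be narrower than the finding that prompts it. Appendix 4 gives no reason to think so.

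The rule is applied by internists at up to 12 hospitals (Table 1). Depending on which page a site follows, a moderately depressed patient with suicidal thoughts could stay on a reduced dose of peg-interferon or be taken off it. Section 7.2.2.2 itself names depression as a common side effect of that drug. An error in either direction has a cost: continued exposure for a patient at risk, or the loss of a treatment that might have cured the infection.

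**Working it through.** The plan gives no figure on this point, so the check sets the two rules side by side.

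**Inputs**
- Rule A, Section 7.2.2.2, read within its paragraph on moderate or severe depression: stop if depression is severe or ideation is active; otherwise evaluate and reduce the dose.
- Rule B, the moderate-to-severe bullet of Appendix 4: stop if symptoms are severe or ideation is present; otherwise evaluate and reduce the dose.
- Mild depression: neither text, read this way, gives a stop instruction.

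**Step 1: suppose 'active' is narrower than 'current'.** There are 3 severities × 3 ideation states = 9 cells.

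| Depression | Ideation | Rule A | Rule B | Same? |
|---|---|---|---|---|
| Mild | none | no stop line | no stop line | yes |
| Mild | present, not active | no stop line | no stop line | yes |
| Mild | active | no stop line | no stop line | yes |
| Moderate | none | reduce | reduce | yes |
| Moderate | present, not active | reduce | **stop** | **no** |
| Moderate | active | stop | stop | yes |
| Severe | any of the three states | stop | stop | yes (3 cells) |

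The rules differ in 1 of 9 cells.

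**Step 2: suppose 'active' means 'current'.** Ideation then has two states, none or present, giving 3 × 2 = 6 cells. The cell that differed no longer exists, and the rules differ in 0 of 6.

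**Step 3: does the protocol choose between these meanings?** It does not define the word for ideation. In Table 4 it uses 'active' for ongoing conditions: rheumatoid arthritis, symptomatic coronary disease, drug or alcohol abuse. That favours 'current'. Against it, ideation found at an evaluation is already current, so the word would add nothing, and it appears directly after a sentence that does without it. Neither reading can be excluded.

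**Step 4: does the protocol say which text governs?** No sentence does. The column heading in Appendix 4 speaks of recommendations, but the same appendix also carries mandatory stopping rules for laboratory values, so the label alone does not rank the depression row below Section 7.2.2.2.

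The cells are a count of situations, not of patients. The documents give no frequency for ideation.

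**The case against.** The best reply is that the protocol uses 'active' elsewhere to mean ongoing and never separates active from passive ideation, so the two rules coincide. Depression also has its own section in mandatory language, while the body text cites Appendix 4 only under other adverse events and as recommendations, which suggests that Section 7.2.2.2 governs. Even on the unfavourable reading, the patient gets a mental-health evaluation and a dose reduction. A Beck score above 20 is reported at once, the protocol team can be consulted, and Section 7.1.3 permits stopping. A site that stops treatment breaches neither text.

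Much of this stands, and it is why the point is narrow. It does not remove it. The 'ongoing' reading is possible but leaves the word idle, and the placement of the cross-reference hints at precedence without stating it. The safeguards bring the patient to attention without saying whether to stop.

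A reader might go further and infer a second conflict, in mild depression with active ideation, by taking the Section 7.2.2.2 sentence to apply at every severity. The layout speaks against that. In both texts the stop line sits in a block on moderate or severe depression, apart from the mild one, and neither text tells staff to continue treatment in such a patient. The mild bullet in Appendix 4 also sends patients who feel in danger to an emergency room and provides for closer monitoring and specialized advice.

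**Conclusion.** The inconsistency is real and small. It concerns one patient profile, moderate depression with ideation judged not active, and amounts to 1 of 9 cells, or 0 of 6 if 'active' means 'current'. The result rests on two assumptions: that each stop line is confined to moderate or severe depression, as its position indicates, and that 'active' may be narrower than 'current', which the protocol leaves open. It deserves correction because it concerns stopping for suicidal ideation and the repair is a single word.

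Two stronger conclusions are not supported. A reader might infer that sustained response or the premature-discontinuation estimate would be distorted; the documents give neither the frequency of such patients nor any information on which text sites would follow, so no effect on an endpoint can be claimed. A reader might also infer that treatment ought to stop for any ideation at any severity. Neither text says so now, and that would be a new clinical rule.

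**What to change.** At the next amendment, delete 'active' from the stop sentence in Section 7.2.2.2 so that it carries the same, more protective trigger as Appendix 4. If the clinical team does intend the narrower trigger, add 'active' to the Appendix 4 line and give the same one-line definition in both places. Send the sites a short note with the aligned wording. Do not extend the mandatory stop to ideation in mild depression by default; leave that to the clinical team.

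The cost is a change of wording, with no added visits or tests. Section 8.3.1 requires modifications to be approved before use by the national committee, the university committee and each hospital. Assuming one local review for each of the 12 sites in Table 1, that is up to 1 + 1 + 12 = 14 reviews, so the change should travel with others. The clinical downside is possibly a few more early stops of potentially curative treatment.
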